8.3. Variables

The outcome variables for the objective(s) are time to treatment failure (from start of treatment to progression or permanent discontinuation), overall survival (from start of treatment to the date of last follow up or death), therapeutic response to therapy based on response evaluation criteria in solid tumors (RECIST version 1.1), and safety (type, incidence, severity of adverse events graded by the National Cancer Institute [NCI] CTCAE V.4.03)

Variable	Role	Data source(s)	Operational definition
Age, gender, height, weight, blood pressure, socio-demographic characteristics	Baseline characteristic	Medical Records	
Concomitant diseases	Baseline Characteristic	Medical Records	
Medication	Baseline Characteristic	Medical Records	
Histopathological findings	Baseline Characteristic	Medical Records / Pathology Reports	
Surgical Operations	Baseline Characteristic	Medical Records	
The cytokine (interferon alpha) usage in the first-line treatment, TKI usage in the 2 nd line treatment and the dosage and the duration of the treatment	Baseline Characteristic	Medical Records	
Metastatic features	Baseline Characteristic	Medical Records	
MSKCC risk factors	Baseline Characteristic Follow-up Characteristic	Medical Records	
3 rd line treatment	Baseline Characteristic Follow-up Characteristic	Medical Records	

	Close-out Characteristic		
The performance score before the second and third-line treatment		Medical Records	
The quality of life questionnaire (FKSI-15, EQ5D-3L, FKSI-DRS) on each visit	Baseline Characteristic Follow-up Characteristic Close –out Characteristic	Patient interview	
Blood pressure		Patient diary	
Other treatment during follow-up, if any, the dose and the duration	Follow-up Characteristic	Medical Records	
Treatment of the side effects, interruption of the treatment, dose reduction, dose-elevation	Baseline Characteristic Follow-up Characteristic	Medical Records	
Duration of PFS, OS and ORR	Follow-up Characteristic Close-out Characteristic	Medical Records	

Schedule Procedure	Initial visit	Follow-up 3.month	Follow-up 6.month	Follow-up 9.month	Follow-up 12.month	Survival Follow-up
Demographic data	X					
Histopathological Findigs	X					
Medical history	X					
Previous therapy of mRCC	X					
MSKCC Risk Factors	X	X	X	X	X	
Surgical Operations	X					
Metastases Information	X					
FKSI-15, EQ5D-3L, FKSI-DRS Questionnaire	X	X	X	X	X	
Evaluation of PFS,OS and ORR		X	X	X	X	
Concomitant medication	X	X	X	X	X	
Visit date	X	X	X	X	X	
ECOG and Karnofsky Performance Status	X	X	X	X	X	
Prescribed TKI and dose	X					
3 rd line treatment	X	X	X	X	X	
Assessment of Response		X	X	X	X	
Adverse Events (Serious Adverse Events must be reported to the sponsor within 24 hours)		X	X	X	X	
Survival status						X

8.4. Data sources

The source of the data will be the electronic or the written patient records of the participating centers. The patient records form the basic source for the information about the state of a patient's health. For this reason, all the data of the patient are archived in various ways in the center. One of the most commonly used data source is the computer-based patient record system. The patient data can be accessed using these systems generated with various computer programs.

Another common use in the hospital is the hard-copy filing system in the form of log file. The patient's data can be accessed through a patient file with a specific code number. In the centers, both systems can be used in conjunction.

The data can be accessed using both systems.

8.5. Study size

Since this is a multi-center post-marketing observational study, there is no hypothesis to be tested. In this study, patients with metastatic renal cell carcinoma from centers in 12 NUTS regions of Turkey will be included, who meet the inclusion criteria. Since this is a non-interventional observational study, there is no specific follow-up protocol. In this study, approximately 152 patients will be evaluated.

According to Turkish Statistical Institute data at the end of 2013, Turkey population is approximately 80 million [5]. In the project of Turkey Association of Cancer Research Control which was named Cancer Record and Incidence shows that cancer incidence is 100-150 in 100.000 [6] and 2% of all new cancers are renal cell carcinoma [7]. There would be 1800 new RCC patients in 1 year, and according to the OS of the disease, there would be 4000 RCC patients in Turkey. 15% of these are metastatic at the time of diagnosis and 30-40% [8] of these are metastatic after a period of a time. Presuming that there are 1800 patients with metastatic renal carcinoma in Turkey, the minimum sample size with 7,6 confidence interval, 95% confidence level and 80% power was calculated as 152.

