- Correlation between efficacy (overall response rate at month 12 and median PFS) and dose modifications due to adverse events
- Correlation between efficacy (overall response rate at month 12 and median PFS) and blood pressure

Study Design

This is a multi-center, national, non-interventional/observational study. It has been defined according to the NUTS (Nomenclature of Territorial Units for Statistics: Nomenclature d'unités Territoriales Statistiques, French) criteria, which is a regional classification, created in order to reduce interregional disparities in socio-economic analysis of the regions, and to produce data comparable to that of the European Union (EU). Turkey has been divided into 12 NUTS regions depending on the economic, social, cultural, and geographical aspects, and the population size. In this study, patients with metastatic renal cell carcinoma from centers in 12 NUTS regions of Turkey will be included, who meet the inclusion criteria. In this study, approximately 152 patients planned to be recruited in 12 months and followed-up for 12 months. Additionally, every patient will be followed-up once for survival follow-up in order to assess the overall survival before the site close out visit. Survival follow-up will be performed via telephone visit or site visit if exist.

Study Population

Metastatic renal cell carcinoma patients under 3rd line targeted therapy following 1st line interferon alpha and 2nd line TKI. All patients will be ≥ 18 years old and have signed the informed consent document.

Variables

Age, gender, height, weight, and vital signs such as blood pressure

Socio-demographic characteristics

ECOG performance status

Concomitant diseases and medication

Medical history

Histopathological findings

Type of the surgical procedure

Treatment history and current treatment information

Metastatic features

MSKCC risk factors

Laboratory findings

The quality of life questionnaire (FKSI-15, EQ5D-3L, FKSI-DRS) on each visit.

Blood pressure diary

Other treatment during follow-up, if any, the dose and the duration

Side effects (treatment of the side effects, interruption of the treatment, dose reduction, dose-elevation)

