8. RESEARCH METHODS

8.1. Study design

This is a multi-center post-marketing observational study. It has been defined according to the NUTS (Nomenclature of Territorial Units for Statistics: Nomenclature d'unités Territoriales Statistiques, French) criteria, which is a regional classification, created in order to reduce interregional disparities in socio-economic analysis of the regions, and to produce data comparable to that of the European Union (EU). Turkey has been divided into 12 NUTS regions depending on the economic, social, cultural, and geographical aspects, and the population size. In this study, patients with metastatic renal cell carcinoma from centers in 12 NUTS regions of Turkey will be included, who meet the inclusion criteria. Since this is a non-interventional observational study, there is no specific follow-up protocol. In this study, approximately 152 patients planned to be recruited in a year and followed-up 12 months.

This is a multi-center post-marketing observational study. In this study, patients with metastatic renal cell carcinoma from centers in 12 NUTS regions of Turkey will be included,

who meet the inclusion criteria. Since this is a non-interventional observational study, there is no specific follow-up protocol.

Presuming that there are 1800 patients with metastatic renal carcinoma in Turkey, the minimum sample size was calculated as 152.

There will be a total of 25 centers in various cities of Turkey.

The centers will consist of medical oncology clinics.

In this study, the patient follow-up period is 12 months. Each patient will be followed up to 5 times; the data will be collected at baseline, the 3rd, 6th, 9th and 12th months according to the routine practice. Additionally, every patient will be followed-up once for survival follow-up in order to assess the overall survival before the site close out visit. Survival follow-up will be performed via telephone visit or site visit if exist.

Because of the observational nature of the study, there is no predefined treatment protocol. The participating physician will continue to treat the patients at his/her own discretion. Frequency of visits will be continued per physician's preference.

The patients will be asked to fill in the quality of life questionnaire (FKSI-15, EQ5D-3L, FKSI-DRS) on each visit.

The assessment of the side effects will be based on the "Common Terminology Criteria for Adverse Events". The CTCAE V.4.03 will be used.

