8.6. Data management

The data will be analyzed using the statistical package program. The categorical variables will be given as number and percentages, and the continuous variables will be presented as averages and standard deviations. For between-group comparisons of categorical variables, the chi-square test will be used. The continuous variables will be tested for normal distribution using the Kolmogorov-Smirnov test and the Shapiro Wilks test. For the normally distributed continuous variables, the parametric tests (the t-test, the ANOVA, the repeated measures analysis of variance, etc.), and for the continuous variables without a normal distribution, the non-parametric tests (the Mann-Whitney U test, the Kruskal Wallis analysis of variance, the Friedman Analysis of Variance, etc.) will be used. The level of significance will be taken as $p = 0.05$.

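### The 7.6-point margin for 152 patients depends on a finite-population correction that does not fit the study; without it the margin is at most 7.95 points

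*Combined protocol and SAP*

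**What the plan says.** Section 8.5, and in the same terms the Sample Size part of the Abstract, states: "Presuming that there are 1800 patients with metastatic renal carcinoma in Turkey, the minimum sample size with 7,6 confidence interval, 95% confidence level". The sentence ends with the result: "95% confidence level and 80% power was calculated as 152". Section 8.1 repeats the 1800 and the 152 without the margin. No endpoint, expected proportion, formula or unit for the 7.6 is given.

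The 1800 follows estimates of about 4000 renal cell carcinoma patients in Turkey, of whom "15% of these are metastatic at the time of diagnosis and 30-40% [8] of these are metastatic after a period of a time". It is not limited by treatment line, and no count of third-line patients is given.

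The Abstract defines the study population as "Metastatic renal cell carcinoma patients under 3rd line targeted therapy following 1st line interferon alpha and 2nd line TKI". Section 8.2 requires progression on a TKI after interferon alpha, and section 8.2.1 allows at most one month of third-line treatment before entry. On recruitment, section 8.1 says: "There will be a total of 25 centers in various cities of Turkey". No random selection of centres or patients is described. Section 8.5 also says that the study tests no hypothesis.

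**The concern.** A population size enters a precision calculation only through a finite-population correction. That correction is right when a simple random sample is drawn from a fixed, listed population and the conclusions concern that list. None of this matches the study:

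- The population counted (all metastatic patients) is not the population sampled (patients starting third-line therapy).
- Patients come from participating oncology centres, with no described random selection from the 1800.
- The objectives concern quality of life, response and progression-free survival with third-line therapy. That is inference about how treatment performs, including in future patients, and not a census of people alive with the disease at one time.

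With no hypothesis to test, precision is the only quantitative justification for the study size. A reader would take 7.6 points as the margin that 152 patients give for a third-line outcome. At the planning value that reproduces 152, they do not.

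**Working it through.** **Inputs from the documents.** Margin e = 7.6, read as plus or minus 7.6 percentage points; 95% confidence, z = 1.96; N = 1800; n = 152; 25 centres. The 1800 equals 4000 × (15% + 30%).

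**Inferred inputs.** Proportion p = 0.5, and use of a finite-population correction.

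**Step 1: reproduce 152.**

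- Without correction: n0 = z²p(1−p)/e² = 1.96² × 0.25/0.076² = 0.9604/0.005776 = 166.3.
- With correction: n = n0/[1 + (n0 − 1)/N] = 166.27/(1 + 165.27/1800) = 152.3.

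This matches the stated 152. Other readings do not: N = 4000 gives 159.7; 7.6 as the full width gives 665 (486 with the correction at N = 1800); a one-sided z gives 117 (110); adding a term for 80% power, two-sided, gives 340 (286). The power figure therefore plays no part in the 152.

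**Step 2: remove the correction.**

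- Half-width at n = 152, p = 0.5: 1.96 × √(0.25/152) = 7.95 points.
- With the correction it is 7.95 × √[(1800 − 152)/1799] = 7.61 points.
- A margin of 7.6 without the correction needs 166.3, rounded up to 167 patients, which is 15 more than planned.

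**Step 3: dependence on the proportion (n = 152, no correction).** The half-width is 7.6 or less when p(1−p) ≤ 0.076² × 152/1.96² = 0.2285, that is, for p up to about 0.35 or from about 0.65.

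| p | Half-width (points) |
|---|---|
| 0.50 | 7.95 |
| 0.30 | 7.29 |
| 0.20 | 6.36 |

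**Step 4: effect of a smaller N.** If the correction is kept at n = 152 and p = 0.5, the half-width is 7.61 for N = 1800, 7.25 for N = 900, 6.87 for N = 600 and 5.59 for N = 300. The values below 1800 are illustrations, since the documents give no third-line count.

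**Step 5: what could widen the margin (all rates assumed; p = 0.5, no finite-population correction).**

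- If 10% or 20% of patients are not evaluable: 8.4 or 8.9 points.
- With correlation within centres: mean centre size m = 152/25 = 6.08 and design effect 1 + (m − 1) × ICC. For ICC 0.02, 0.05 and 0.10 the design effect is 1.10, 1.25 and 1.51, and the half-width 8.3, 8.9 and 9.8 points.

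The two sources are shown separately, not combined.

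**The case against.** The strongest defence is that little is lost. Going from 7.61 to 7.95 points changes no conclusion in a study that calls itself mainly exploratory and descriptive. The 7.95 is also a worst case: for a response rate of 35% or less, 152 independent patients meet 7.6 with no correction at all. Both points stand. They limit the size of the problem but do not make the derivation valid, and since the plan names no endpoint or expected proportion, it cannot claim the favourable case.

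Three stronger readings are tempting, and the documents do not support them.

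- *Counting all treatment lines overstates the precision.* The reverse holds within the plan's own formula: a smaller third-line population would narrow the interval (step 4). The 1800 is the wrong frame, but the loss comes from the correction being inapplicable.
- *Clustering and missing data make the true margin 8.3 to 9.8 points.* These figures rest on assumed ICCs and drop-out rates, and the documents give neither. Section 8.5 speaks of 152 patients evaluated, while the Abstract's Study Design part and section 8.1 speak of 152 recruited. Section 8.7 asks only for some efficacy information, so the loss cannot be sized.
- *The planned intervals are too narrow and must be adjusted for centre.* Section 8.7 specifies 95% limits only for Kaplan-Meier quantities, names no variance method, and plans no interval for response rate or quality of life. Intervals that ignore centre would be too narrow only if outcomes are positively correlated within centres. That is plausible where treatment is left to the physician, but it is not shown.

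**Conclusion.** The point holds in a limited form. The 152 is arithmetically reproducible, but the 7.6 attached to it is not supported for the question the study asks. For a proportion, 152 independent evaluable patients give a 95% half-width of at most 7.95 points, about 0.35 points above the stated figure.

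This rests on two inferences (p = 0.5 and the finite-population correction) that are not stated in the plan; of the readings tried, only this combination returned 152. It also rests on reading 7.6 as a half-width in percentage points. It does not show that 7.6 is missed for every outcome, and it does not show that the study is too small. Among the primary objectives the margin applies directly only to the response rate, since a quality-of-life score and a median time are not proportions.

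**What to change.** In sections 3, 8.1 and 8.5, remove the 1800-patient population as the basis for the sample size. In sections 3 and 8.5, give the precision as: '152 evaluable patients give a 95% CI half-width of at most 8.0 percentage points for a proportion, assuming independent patients; non-evaluable patients or correlation within centres would widen it.' Section 8.1 can carry the same sentence or refer to 8.5.

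Do not change the number of patients. If the protocol shows figures for non-evaluable patients or within-centre correlation, it should label the rates as assumptions. Intervals for the response rate or Kaplan-Meier estimates that treat centre as the cluster are an optional sensitivity analysis, not a required change.

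The cost is a wording change in three places and a slightly less favourable stated margin. No new data are needed.

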8.2.1. Inclusion criteria

Patients must meet all of the following inclusion criteria to be eligible for inclusion in the study:

- Histologically confirmed metastatic renal cell cancer patients who have already been using targeted therapies for up to 1 months as 3rd line treatment
- Patients 18 years and older than 18 years
- Evidence of a personally signed and dated informed consent document indicating that the patient (or a legal representative) has been informed of all pertinent aspects of the study.

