8.7. Data analysis

Statistical analyses will be primarily of explorative and descriptive nature. All issues concerning patient validity, data consistency checks, permissible data modifications will be described in detail in the Data Management Plan.

Patients who took at least one dose of 3rd line treatment and have sufficient information whether they had an adverse event or not will be valid for safety analysis. Patients who took at least one dose of 3rd line treatment and have any information regarding efficacy of 3rd line treatment will be valid for intent-to-treat efficacy analysis.

Demographic data, baseline characteristics, diagnosis and prior treatment of RCC, concomitant diseases, and concomitant medication will be described with summary statistics such as mean, SD, minimum, 1, 5, 25, 75, 95, 99 percent quartiles, median, maximum for continuous variables, and category counts and frequencies (percentages) for

categorical variables. Concomitant diseases on the case report form correspond to MedDRA terms. Concomitant medication will be coded using WHO's drug dictionary.

Descriptive summaries of Kaplan-Meier (KM) estimates (including number of failed, number censored, 25th and 75th percentiles with respective 95% confidence level and median with 95% confidence level) and KM curves will be presented for time-to-event efficacy variables (PFS, TTP, time to treatment failure). Mean, SD, minimum, 1, 5, 25, 75, 95, 99 percent quartiles, median, maximum will be produced for duration of TKI treatment. Category counts and frequencies (percentages) will be calculated for tumor status at different visits and general subjective rating of efficacy of TKI from the treating physician.

Adverse events will be summarized using the MedDRA and the CTCAE coding system. Event rates for single adverse events will be calculated based on the total number of patients valid for safety. Adverse events will be categorized according to relation, seriousness, CTCAE grade (version 4.03), and discontinuation of therapy, action taken and outcome. Serious adverse events and unexpected or unlisted ADRs will be evaluated separately.

Category counts and frequencies (percentages) will be calculated for overall tolerability.

The factors, which might have impacted the duration of treatment, will be studied by retrospectively.

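### The 80% power attached to the sample size of 152 refers to no test: 152 fits a precision formula with no power term, and Section 8.5 says no hypothesis is tested

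*Combined protocol and SAP*

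**What the plan says.** Section 8.5 (Study size) presumes 1,800 patients with metastatic renal carcinoma in Turkey and states that "the minimum sample size with 7,6 confidence interval, 95% confidence level and 80% power was calculated as 152". The Sample Size part of the abstract (Section 3) repeats this. Section 8.5 also says that, because the study is observational, "there is no hypothesis to be tested"; the abstract does not carry that sentence. Neither place gives an endpoint, an expected proportion, a null value, an effect size or a standard deviation for the 152.

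Section 8.6 (Data management) plans significance tests at p = 0.05: "For between-group comparisons of categorical variables, the chi-square test will be used", with t-tests, ANOVA and non-parametric tests for continuous variables. Section 8.7 (Data analysis) says "Statistical analyses will be primarily of explorative and descriptive nature".

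On who is sampled, Section 8.2.1 admits patients who "have already been using targeted therapies for up to 1 months as 3rd line treatment", and Section 8.1 says "There will be a total of 25 centers in various cities of Turkey".

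**The concern.** Power is the probability that a given test rejects a given null hypothesis under a given alternative. With no hypothesis, test or effect size, a power of 80% has no meaning. The rest of the sentence (an interval of 7.6, a 95% level, a population of 1,800) describes a precision calculation.

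This is the study's only sample-size justification, and it claims a property the design does not have. Section 8.7 calls the analyses only primarily explorative. A reader who sees 80% power in Section 8.5 and tests at p = 0.05 in Section 8.6 could take a non-significant comparison as adequately powered evidence of no difference.

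A smaller issue comes with it. Reaching 152 appears to need a finite-population correction based on all 1,800 presumed metastatic patients. The study enrols only patients early in third-line treatment, at 25 centres, and describes no random sampling from the 1,800.

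**Working it through.** **Inputs.** From Section 8.5: n = 152; "7,6 confidence interval", read as a half-width of 7.6 percentage points (no unit is given, nor whether it is half or full width); "95% confidence level", so z = 1.96; N = 1,800; stated power 80%. Inferred, not in the documents: p = 50%, the usual worst case, and the use of a finite-population correction.

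**1. Reproducing 152 from precision alone.**

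- n0 = z² p(1−p)/e² = 1.96² × 0.25 / 0.076² = 166.3
- n = n0 / (1 + (n0 − 1)/N) = 166.3 / (1 + 165.3/1800) = 152.3

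This matches 152 without any power term. Omitting the correction leaves 166.3. Reading 7.6 as a full width (e = 0.038) gives 486 with the correction and 665 without. Neither fits.

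**2. Adding 80% power.** Replacing 1.96 by 1.96 + 0.84 (two-sided 5%, 80% power) gives 339.7 without the correction and 285.9 with it. The one-sided versions give 267.6 and 233.1. None is near 152.

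**3. Power that 152 patients would give.** The documents define no comparison, so these are illustrations on assumed values.

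- One sample, assumed null 50% against 57.6%, two-sided 5%: power = Φ[(0.076 − 1.96 × √(0.25/152)) / √(0.576 × 0.424/152)] = Φ(−0.087) ≈ 47%.
- Two groups, 46.2% against 53.8%, pooled-variance test, two-sided 5%. Group splits are assumed. The standardised mean difference is 2.80 × √(1/n1 + 1/n2).

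| Split | Power for 7.6 points | Difference around 50% with 80% power | Mean difference with 80% power |
|---|---|---|---|
| 76 / 76 | 15% | 22.5 points | 0.45 SD |
| 106 / 46 | 14% | 24.4 points | 0.49 SD |
| 122 / 30 | 11% | 27.9 points | 0.57 SD |

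**4. Precision that 152 patients do give.** The half-width is 1.96 × √(p(1−p)/n), multiplied by √((N − n)/(N − 1)) if corrected.

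- p = 50%, N = 1,800: 7.61 points. Uncorrected: 7.95 points, a difference of about 0.35.
- Uncorrected, the half-width equals 7.6 at p of about 35% or 65%, so it exceeds the stated figure only between those values. At an assumed response rate of 10% it is 4.8 points.
- If the correction were kept with a smaller third-line population, the interval would narrow: 7.25 points at an assumed N = 900 and 6.6 at N = 500.

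**5. Precision with assumed losses, uncorrected.** For a mean, the half-width in SD units is 1.96/√n.

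| Assumed loss | Evaluable n | p = 50% | p = 10% | QoL mean |
|---|---|---|---|---|
| 0% | 152 | 7.95 points | 4.8 points | 0.16 SD |
| 10% | 137 | 8.4 points | 5.0 points | 0.17 SD |
| 20% | 122 | 8.9 points | 5.3 points | 0.18 SD |
| 30% | 106 | 9.5 points | 5.7 points | 0.19 SD |

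**The case against.** The strongest objection is that the 50% is inferred and is not the only value that fits. A two-sided 5% one-sample test of about 10.9% against 18.5%, a 7.6-point difference, has 80% power at n = 152 without any correction. That arithmetic is right. But this null value appears nowhere in the documents, and the reading leaves the 1,800 unused and contradicts the statement that nothing is tested. The precision reading needs one conventional assumption and uses every other printed input. In either case the documents do not say what the 80% refers to.

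Second, the two-group figures rest on invented splits, and the plan never presents 7.6 points as a difference to detect. That is correct. They show what a test under Section 8.6 could deliver at this size and measure nothing the plan promises.

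Third, the plan limits the harm itself: it calls the analyses primarily explorative, says no hypothesis is tested, and in Section 8.1 repeats the 152 without mentioning power. This lowers the stakes. It does not remove a false statement from the abstract, where the sentence disclaiming a hypothesis is missing, or make Section 8.6 say that its tests are unpowered.

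Fourth, the finite-population correction is a separate and minor matter. Its effect is indeed small, at most about 0.35 points, and a smaller population would narrow the interval. It belongs here only because restating the precision basis requires saying whether the correction applies.

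**Conclusion.** The concern holds. The conflict between a stated power and the absence of any hypothesis is on the page and needs no assumption. That 152 came from a precision formula is an inference from p = 50%, a half-width reading of 7.6 and a correction for 1,800; it reproduces the figure (152.3), whereas adding 80% power to those inputs gives 286 or 340.

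This is an error in the justification and leaves the sample size itself intact. As a precision-based size, 152 stands, with a worst-case half-width of 7.95 points uncorrected, or 7.6 if the correction is justified. No estimate, analysis set or procedure changes. It should be corrected before results are reported, because the power claim could lend unearned weight to non-significant tests.

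**What to change.** - **Abstract (Section 3) and Section 8.5:** delete the reference to 80% power. If a test really was intended, name it with its null value and effect size, and reconcile it with the statement that no hypothesis is tested.
- **Same places:** state the precision basis. Name the endpoint (response rate is the only proportion among the primary objectives), the assumed proportion and the half-width: at most 7.95 points with 152 patients, or 7.6 if the finite-population correction is kept and justified. Add about 0.16 SD for a baseline quality-of-life mean, since quality of life is the first-listed primary objective.
- **Optional:** one line giving the precision for 137, 122 and 106 evaluable patients, as tabulated above, with the loss rates labelled as assumptions.
- **Section 8.6:** state that the tests at p = 0.05 are exploratory and unpowered, and that a non-significant result is not evidence of no difference.

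The cost is text in three places. No extra patients or data are needed. If the correction is dropped, the stated worst-case precision at n = 152 becomes up to 0.35 points less favourable.

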7. RESEARCH QUESTION AND OBJECTIVES

Research Question:

In this study, different from other studies in the literature, the data will be collected to observe the quality of life and efficacy after first line interferon alpha and second line TKI treatments.

Primary Objective:

- Measurement of health-related quality of life with targeted therapy used as 3rd line.
- Overall response rate at the end of follow up
- Median progression free survival according to RECIST version 1.1

Secondary Objectives:

- Overall survival rate
- Effect of quality of life on prognosis.
- Adverse events during 3rd line targeted treatment according to CTCAE.4.03
- Dose modifications due to adverse events
- Correlation between efficacy (overall response rate at month 12 and median PFS) and dose modifications due to adverse events
- Correlation between efficacy (overall response rate at month 12 and median PFS) and blood pressure

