9.2. Patient withdrawal

Patients may withdraw from the study at any time at their own request, or they may be withdrawn at any time at the discretion of the investigator or sponsor for safety, behavioral, or administrative reasons. In any circumstance, every effort should be made to document subject outcome, if possible. The investigator should inquire about the reason for withdrawal and follow-up with the subject regarding any unresolved adverse events.

If the patient withdraws from the study, and also withdraws consent for disclosure of future information, no further evaluations should be performed, and no additional data should be collected. The sponsor may retain and continue to use any data collected before such withdrawal of consent.

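### Section 8.5 uses 152 as the calculated minimum, the number recruited and the number evaluated, so at the 50% rate that reproduces it the ±7.6-point precision has no room for any non-evaluable patient

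*Combined protocol and SAP*

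**What the plan says.** The number 152 has three roles in the protocol.

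- **Calculated minimum.** Section 8.5 states that "the minimum sample size with 7,6 confidence interval, 95% confidence level and 80% power was calculated as 152", taking 1800 patients with metastatic disease as the population. The abstract repeats this calculation, and Section 8.1 repeats the minimum.
- **Number recruited.** The abstract has "approximately 152 patients planned to be recruited in 12 months and followed-up for 12 months". Section 8.1 has "approximately 152 patients planned to be recruited in a year and followed-up 12 months".
- **Number evaluated.** Section 8.5 has "In this study, approximately 152 patients will be evaluated", and the abstract says the same.

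Two other sections provide for patients who will not contribute. Section 9.2 says "Patients may withdraw from the study at any time at their own request". Section 8.7 admits to the efficacy analysis only those dosed patients who "have any information regarding efficacy of 3rd line treatment will be valid for intent-to-treat efficacy analysis".

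No rate of withdrawal, death or non-evaluability is given anywhere, and nothing is added to 152 for it. Section 8.5 does not say which endpoint, rate or visit the 7.6 refers to.

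**The concern.** A calculated minimum is the number of patients who must supply a value for the stated precision to be reached. If the same number is recruited, the precision is reached only if every recruited patient is evaluable. The protocol's own provisions for withdrawal and for missing efficacy information say that this need not happen.

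What is at stake is how the results are read. Section 7 puts "Overall response rate at the end of follow up" under the primary objective, and Section 8.7 plans percentages for tumour status at different visits. A reader who takes 7.6 points as the precision of every such percentage may place more weight on it than the number of contributing patients supports. Nothing in Section 8.5 warns against this.

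**Working it through.** **Inputs from the protocol (Section 8.5):** precision 7.6, confidence 95%, population N = 1800, stated n = 152.

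**Inferred, not stated:** 7.6 is a half-width in percentage points, the interval is two-sided (z = 1.96), and the planning proportion is p = 0.5.

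**Step 1. Reproduce 152.**

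- Without correction: n0 = z² × p(1 − p) / d² = 1.96² × 0.25 / 0.076² = 166.3.
- With finite-population correction: n = n0 / [1 + (n0 − 1)/N] = 166.3 / (1 + 165.3/1800) = 152.3, printed as 152.

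Other readings do not give 152. Omitting the correction gives 167. Taking 7.6 as the full width gives 665 before correction. Bringing in 80% power gives 340, or 286 with correction. So 152 is a precision figure alone, with no term for loss.

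**Step 2. Check for headroom.** The half-width is h = 1.96 × √[p(1 − p)/n] × √[(1800 − n)/1799]. At p = 0.5 and n = 152, h = 7.61 points. There is no reserve, so any reduction in n takes h further above 7.6.

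**Step 3. Size of the shortfall at p = 0.5.** The loss rates are assumed, because the plan gives none.

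| Assumed loss | Evaluable of 152 | Half-width (points) | Relative to 7.61 |
|---|---|---|---|
| 0% | 152 | 7.61 | – |
| 5% | 144 | 7.84 | 3% wider |
| 10% | 137 | 8.05 (8.0 to one decimal, from 8.0499) | 6% wider |
| 20% | 122 | 8.57 | 13% wider |
| 30% | 106 | 9.24 | 21% wider |

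**Step 4. Dependence on the true rate.** The same formula with p below 0.5:

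| True rate | n = 152 | n = 122 (20% loss) | n = 106 (30% loss) |
|---|---|---|---|
| 10% | 4.56 | 5.14 | 5.54 |
| 20% | 6.09 | 6.86 | 7.39 |
| 30% | 6.97 | 7.85 | 8.47 |
| 50% | 7.61 | 8.57 | 9.24 |

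At 20% loss, 7.6 is exceeded only for rates between about 27% and 73%. At 30% loss the range is about 22% to 78%.

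**Step 5. Which results the figure can cover.** A half-width for a proportion applies to response rates and to tumour-status percentages. It does not apply to mean quality-of-life scores. Nor does it apply to median PFS, which Section 8.7 estimates by Kaplan-Meier.

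**The case against.** The case for leaving the text alone has several parts.

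- **The study is descriptive.** Section 8.5 says there is no hypothesis to test, the target is approximate, and the printed calculation reproduces. This stands. The defect is an unstated assumption of complete evaluability, not an arithmetic slip, and no analysis changes because of it.
- **Most primary results are little affected by death.** The abstract and Section 8.7 define best overall response over the whole treatment period, so a patient who dies after a response assessment stays in the denominator. Under Section 8.1, death is an event for PFS and OS. This also stands. For best overall response the loss is confined to patients without efficacy information, and the widening is modest if they are few.
- **Rates away from 50% can still meet 7.6.** This is true, as Step 4 shows. It limits the point without removing it, because the plan names no rate and the printed 152 reproduces at 50%.

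Two stronger readings are tempting, and the documents support neither.

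- A reader might infer heavy 12-month mortality from the national figures in Section 8.5: "There would be 1800 new RCC patients in 1 year, and according to the OS of the disease, there would be 4000 RCC patients in" (the whole country). Dividing 4000 by 1800 gives a mean of about 2.2 years. That ratio covers renal cell carcinoma of all stages. Turning it into a month-12 count for third-line metastatic patients needs a steady state, a constant hazard and the same hazard in both groups. The protocol states none of these and gives no 12-month survival rate.
- A reader might infer that 7.6 points was promised for quality of life at month 12 and is not delivered. Section 8.5 ties 7.6 to no visit or endpoint. Section 8.6 summarises continuous variables by means and standard deviations, and the protocol defines no quality-of-life categories.

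**Conclusion.** The point holds in a limited form. The minimum, the recruited number and the evaluated number cannot all be 152 unless every patient is evaluable, and the protocol itself foresees that some may not be. At the 50% rate that reproduces 152, the stated 7.6 points is lost as soon as any patient drops out of the denominator. The half-width becomes 7.8 to 8.6 points under an assumed 5–20% loss, and 9.2 under 30%.

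These sizes rest on the inferred p = 0.5, on the correction for 1800 taken as it stands, and on loss rates that are assumed. They do not carry over to proportions far from 50%, to mean scores or to median PFS. Visit-specific proportions, such as tumour status at month 12, will be less precise because deaths and withdrawals reduce n. The documents do not allow that reduction to be quantified. The text should be corrected, but the validity of the analysis is not in question.

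**What to change.** In Section 8.5 and the matching text of the abstract:

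1. Keep 152 as the number recruited, and stop stating that 152 will also be evaluated.
2. Name the proportion endpoint and the assumed rate behind 7.6, and say that it is a 95% half-width in percentage points.
3. State the expected evaluable number for that endpoint, the loss assumed and the resulting half-width. For best overall response, for example, an assumed 5–20% loss gives about 122–144 evaluable and 7.8–8.6 points at a rate of 50%. The sponsor should replace the assumed loss with its own expectation.
4. State that 7.6 applies only to a proportion observed in all 152 patients, and that visit-specific proportions, such as tumour status at month 12, will be less precise.

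The cost is that the stated precision becomes slightly less favourable. No extra patients, visits or procedures are needed. The alternative, keeping 152 evaluable by recruiting 152/(1 − loss), would need 160, 169, 190 or 218 patients at 5%, 10%, 20% or 30% loss. It is not proposed here, since the study is descriptive and an accurate statement of precision is enough.
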